11.0 Analyses Sets

All analysis sets will include only subjects who gave informed consent and are summarized in [Table 3](#).

Table 3 Analysis Sets and Definitions

| Analysis Set | Definition | Use | How Analyzed |
|-------------------|---|-------------------------|--|
| Safety | All subjects who have received any amount of study drug | Safety and tolerability | According to actual treatment received |
| PK (Analysis) | All subjects in the Safety Analysis Set who have received at least 1 dose of IMR-687 and have any measurable post-dose IMR-687 concentration-time data | PK concentrations | According to actual treatment received |
| PK (Evaluable) | All subjects in the Safety Analysis Set who have received at least 1 dose of IMR-687 and have at least 4 consecutive non-zero post-dose IMR-687 concentration-time data points. | PK parameters | According to actual treatment received |
| ITT | All randomized subjects | Efficacy/PD | According to randomized treatment assigned |
| ITT | All randomized subjects who had at least 1 VOC in the 12 months prior to randomization and have received at least one dose of study drug | Efficacy/PD | According to randomized treatment assigned |
| Per Protocol (PP) | All subjects in the Safety Analysis Set who had at least 1 VOC in the 12 months prior to randomization, completed at least 1 valid clinical outcomes assessment without major protocol deviations or events that would be expected to affect the analysis and did not discontinue prior to Week 24 for reasons other than AEs | Efficacy/PD | According to actual treatment received |

11.1 Safety Analysis Set

The safety analysis set will include all subjects who have received any amount of study drug and from whom informed consent has been obtained. The safety analysis set will be used to summarize all safety and tolerability data. In safety data summaries, subjects will be analyzed according to the actual treatment they received.

11.2 PK Analysis Set

The PK Analysis Set, will be defined as a subset of the Safety Analysis Set who are randomized, have received at least 1 dose of IMR-687, and have any measurable post-dose IMR-687 concentration-time data. This set will be used to generate the corresponding PK concentration summaries and plots.

11.3 PK Evaluable Set

The PK Evaluable Set will be defined as all subjects in the Safety Analysis Set who are randomized, have received at least 1 dose of IMR-687, and have at least 4 consecutive non-zero post-dose IMR-687 concentration-time data points. The PK Evaluable Set will be used to generate the corresponding PK exposure (parameter) assessments.

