Nausea onset was between 30 and 120 minutes after the oral administration of IMR-687 and generally lasted 2 to 8 hours. Together with the mitigating effects of food intake and the fact that IMR-687 is a P-gp substrate and unlikely to be CNS penetrant, these data are consistent with nausea/emas resulting from a local effect of IMR-687 in the stomach or the gastrointestinal (GI) tract.

IMR-687 administration was not associated with any clinically significant changes in laboratory values, physical examinations (PEs), or standard 12-lead electrocardiograms (ECGs). Of note, IMR-687 did not result in any significant changes in white blood cell (WBC), platelet, or absolute neutrophil counts.

Exposure parameters following single or multiple qd doses of IMR-687 increased with dose in a near dose-proportional manner (e.g., a 4.1-fold increase for a 4.5-fold change in dose).

Administration with food slowed the rate of absorption of IMR-687 (median time to maximum concentration [t_{max}] delayed by approximately 3 hours), which resulted in an approximately 26% decrease in maximum plasma concentration (C_{max}), but no change in overall exposure (area under the concentration-time curve [AUC]). Multiple-dose PK demonstrated that IMR-687 did not accumulate to a significant extent in healthy volunteers (<13%).

4.2.3.2. Phase 2a Study of IMR-687 in Adult Subjects with Sickle Cell Anemia (IMR-SCD-102)

Study IMR-SCD-102 was a phase 2a, randomized, double-blind, placebo-controlled study in adult subjects with HbSS or HbS β^0 thalassemia that was completed in 2020.

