13.2. Analysis Datasets

The safety analysis set will include all subjects who have received any amount of study drug and from whom informed consent has been obtained. The safety analysis set will be used to summarize all safety and tolerability data. In safety data summaries, subjects will be analyzed according to the actual treatment they received.

The PK analysis set will be defined as a subset of the safety analysis set that includes all subjects who are enrolled in the study, have received at least 1 dose of IMR-687, and have any measurable IMR-687 concentration-time data; this set will be used to generate the corresponding PK concentration summaries and plots.

The PK evaluable set will be defined as a subset of the safety analysis set that received at least 1 dose of IMR-687 and has at least 4 consecutive non-zero post-dose IMR-687 concentration-time data points. The PK Evaluable Set will be used to generate the corresponding PK exposure (parameter) assessments.

The intent-to-treat (ITT) set will include all randomized subjects. The ITT set will be used as the primary analysis set to summarize efficacy, PD, and clinical outcome parameters. Subjects will be analyzed according to their randomized treatment assignment.

The modified intent-to-treat (mITT) set will include all randomized subjects who had at least 1 VOC in the 12 months prior to randomization and have received at least 1 dose of study drug. The mITT set will be used for sensitivity analyses of efficacy, PD, and clinical outcome parameters. Subjects will be analyzed according to their randomized treatment assignment.

The per protocol (PP) set will include all subjects of the safety analysis set who had at least 1 VOC in the 12 months prior to randomization, completed at least 1 valid clinical outcomes assessment without major protocol deviations or events that would be expected to affect the analysis and did not discontinue prior to Week 24 for reasons other than AEs. The PP set will be identified based on blinded data prior to unblinding the mITT dataset. The PP set will be used for sensitivity analyses of efficacy, PD, and clinical outcome parameters.

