13.5.9.2 Plasma Pharmacokinetic Parameters

Plasma PK parameters for IMR-687 will be estimated using noncompartmental methods with Phoenix® WinNonlin® Version 8.1 (Certara, USA). The PK parameters will be estimated from the concentration-time profiles, and AUCs will be calculated using a linear up/log down method using actual sampling times.

The apparent terminal elimination half-life, $T_{1/2}$, where determinable, will be calculated as the natural log of 2 divided by the terminal phase rate constant, λ_{daz} . The number of data points included in the regression will be determined by visual inspection, but a minimum of 3 data points in the terminal phase, excluding C_{max} , is required to estimate λ_{daz} . In order for λ_{daz} and λ_{az} derived parameters (AUC_{inf} , $T_{1/2}$, V_z/F , CL/F (single dose), and V_z/F to be reported, the adjusted r^2 value reported in Phoenix® WinNonlin® must be ≥ 0.80 .

For the purposes of estimating the PK parameters, BLQ values will be set to zero prior to the first measurable concentration and set to missing thereafter, including embedded BLQs. Scheduled sampling times will be used for the interim analyses and actual sampling times will be used for the final analysis.

Missing concentration-time data will be treated as missing except for the pre-dose plasma concentrations where a value of 0 will be imputed for Study Day 1 for the purposes of PK parameter estimation. Similarly for the Week 4 visit, missing concentration-time data will be treated as missing except for the pre-dose concentration following steady state dosing where the lowest concentration value over the dosing interval (C_{min}) will be used for imputation purposes. In addition, subjects must have a 24-hour PK sample collected at Study Day 1 and Week 4 in order to be included in the evaluation of accumulation ratio (RAUC). No extrapolation of AUC_{0-24} for any missing 24-hour PK sample will be performed.

For the final analysis, if the actual time is missing, the scheduled sampling time will be substituted and flagged. Subjects must have at least 4 consecutive non-zero post-dose plasma concentrations in order for their data to be considered evaluable. Profiles that do not meet this criterion will be flagged for exclusion.

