| C _{trough} | Concentration at the end of the dosing interval. |
| AUC ₀₋₂₄ | Area under the concentration-time curve from time 0 to 24 hours post-dose. |
| Lambda _z | Apparent terminal elimination phase rate constant. |
| CL _{ss} /F | Apparent total body clearance from oral administration at steady state, calculated as Dose/AUC ₀₋₂₄ . |
| V _z /F | Apparent volume of distribution from oral administration at steady state, calculated as Dose/lambda _z × AUC ₀₋₂₄ |
| RAUC | Accumulation ratio, calculated as AUC ₀₋₂₄ (Week 4)/ AUC _{last} (Study Day 1; AUC _{last} t = 24 hours). |

C_{last} = last observed measurable plasma concentration

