^l QoL assessments include the specified components of the ASCQ-Me[®], PROPr, SCSES. The translated QoL assessments from PROPr will be used when available.

^m At the Day 1 and Week 4 visits, serial blood samples for IMR-687 (including metabolites and HU, if applicable) plasma concentrations will be drawn pre-dose (within 30 minutes) and at 15 minutes (\pm 5 minutes), 30 minutes (\pm 5 minutes), and 3 hours (\pm 20 minutes) after administration of study drug. A trough blood sample will be drawn pre-dose at Week 24 and on the last day of dosing (Week 52). The date/time of the last administered dose will be recorded. Patients dosed prior to protocol version 4.0 (08 Apr 2021) used the following PK sampling schedule: At the Day 1 and Week 4 visits serial blood samples for IMR-687 plasma concentrations were drawn pre-dose (within 30 minutes) and at 30 minutes (\pm 5 minutes), 1.5 hours (\pm 15 minutes), 6 hours (\pm 1 hour), and 24 hours (\pm 2 hours) after administration of study drug. On these full profile PK days, food details were also recorded at the study sites. A trough blood sample was drawn pre-dose at Week 24 and on the last day of dosing (Week 52).

ⁿ Each study drug bottle will contain 84 tablets. The indicated visits will require 2 bottles to be dispensed.

^o On days when study drug is taken in the clinic, food details will also be recorded.

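### Half-life and the other terminal-rate PK parameters can come only from profiles that peak at the first sample (0.5 h), and the evaluable-set rule tolerates no lost sample

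*SAP*

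**What the plan says.** SAP 11.3 admits to the PK Evaluable Set randomized subjects who received IMR-687 and "have at least 4 consecutive non-zero post-dose IMR-687 concentration-time data points". Protocol 13.2 has the same threshold: a subject qualifies who "has at least 4 consecutive non-zero post-dose IMR-687 concentration-time data points". SAP 13.5.9.2 repeats it ("Subjects must have at least 4 consecutive non-zero post-dose plasma concentrations in order for their data to be considered evaluable") and adds that profiles failing it are flagged for exclusion.

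There are two sampling schedules. The current one (Protocol Table 1 and SAP Appendix 3, footnote m) has post-dose samples at 15 minutes, 30 minutes and 3 hours on Day 1 and at Week 4. The same SAP footnote adds: "Patients dosed prior to protocol version 4.0 (08 Apr 2021) used the following PK sampling schedule", and lists post-dose samples at 30 minutes, 1.5, 6 and 24 hours. SAP 13.5.9 limits noncompartmental analysis to subjects on the earlier schedule. Sparse-schedule data go to descriptive summaries and population PK.

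For the terminal rate constant, SAP 13.5.9.2 requires "a minimum of 3 data points in the terminal phase", not counting Cmax, and an adjusted r-squared of at least 0.80 before lambda_z and the parameters derived from it are reported. On values below the limit of quantification, "BLQ values will be set to zero prior to the first measurable concentration"; later ones are set to missing.

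On absorption, Protocol 4.2.3.1 reports: "Administration with food slowed the rate of absorption of IMR-687". The median tmax moved by about 3 hours. Protocol 9.1 directs subjects to take study drug with food.

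**The concern.** Two rules do not fit the sampling times they are applied to.

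The first is the terminal-phase rule. With only four post-dose samples, three points can follow the peak only if the peak is the first sample. The rule therefore selects profiles by speed of absorption. SAP Table 12 lists lambda_z, half-life, AUCinf, CL/F and Vz/F on Day 1, and lambda_z and Vz/F at Week 4. A table of these values would look like a description of the dosed population but would describe only its fastest absorbers.

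The second is the evaluable rule. It asks for four values from a schedule that yields exactly four. A missing sample, an early value below the limit set to zero, or a later one set to missing each breaks the run. The post-dose provisions for missing and unquantifiable values in SAP 13.5.9.2 can therefore never operate inside an evaluable profile, and usable AUC0-24 values are discarded.

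At stake is the noncompartmental part of the secondary PK objective, exposure to IMR-687. Primary efficacy is not affected.

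**Working it through.** The plan states no figure on this point, so there is nothing to reproduce. The check is a count, with two illustrative calculations.

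**Step 1. Samples against the evaluable rule** (SAP Appendix 3 footnote m; SAP 11.3)

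| Schedule | Post-dose samples per profile | Required | Can a profile qualify? |
|---|---|---|---|
| Before version 4.0 | 4 (0.5, 1.5, 6, 24 h) | 4 | Only with 4 of 4 |
| Current | 3 (0.25, 0.5, 3 h) | 4 | No |

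**Step 2. Points left after the peak, pre-4.0 schedule** (3 required, SAP 13.5.9.2)

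Points left = 4 − position of the Cmax sample.

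| Cmax at | Points left | Lambda_z permitted |
|---|---|---|
| 0.5 h | 4 − 1 = 3 | Yes, if r-squared also passes |
| 1.5 h | 4 − 2 = 2 | No |
| 6 h | 4 − 3 = 1 | No |
| 24 h | 4 − 4 = 0 | No |

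This needs no outside figure.

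**Step 3. Is a peak at the first sample likely when fed?** A delay of about 3 h in median tmax puts the fed median at roughly 3 h or later, whatever the fasted value. As an illustration, a one-compartment oral model was run with assumed half-lives of 4 to 12 h and tmax of 0.25 to 4 h (the documents give neither). The 0.5 h sample is the highest for tmax up to 0.75 h and no longer at 0.9 h. At tmax of 3 h the highest sample is 1.5 h for half-lives of 4 to 8 h and 6 h for a half-life of 12 h. At 3.5 h and above it is 6 h throughout. A typical fed profile would leave 1 or 2 points.

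**Step 4. Cost of the 4-of-4 rule.** If each sample is lost or unquantifiable independently with probability p, the share of profiles retained is (1 − p)^4. Under a rule of at least 3 measurable values including 24 h, it is (1 − p) × [(1 − p)^3 + 3p(1 − p)^2].

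| Assumed p | 4 of 4 | At least 3, including 24 h |
|---|---|---|
| 2% | 0.98^4 = 92% | 0.98 × (0.9412 + 0.0576) = 98% |
| 5% | 0.95^4 = 81% | 0.95 × (0.8574 + 0.1354) = 94% |
| 10% | 0.90^4 = 66% | 0.90 × (0.729 + 0.243) = 87% |
| 20% | 0.80^4 = 41% | 0.80 × (0.512 + 0.384) = 72% |

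The values of p are assumptions; the documents give no rate.

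**Step 5. What does not depend on lambda_z.** By their definitions in SAP Table 12, Cmax, Tmax, AUClast, AUC0-24, CLss/F (dose divided by AUC0-24) and RAUC need no terminal slope. They are available from any complete pre-4.0 profile, and RAUC needs both visits.

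**The case against.** The strongest defence is that the SAP expects gaps. Half-life is to be calculated only where it can be determined, and Table 12 parameters only where feasible. The secondary PK endpoint is the concentration-time profile and population PK, not noncompartmental parameters. Concentration summaries use the PK Analysis Set, which needs only one measurable post-dose value. Individual data are listed, and nothing here is tested. All of this is true and limits the impact. It does not cure the selection: a feasibility clause still allows summary statistics on whichever profiles qualify, and by construction those peak at 0.5 h.

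The documents do not support several stronger readings that a reader might infer:

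- **That current-schedule profiles are lost by mistake.** SAP 13.5.9 excludes them from noncompartmental analysis on purpose. The remaining fault is that SAP 11.3 and Protocol 13.2 do not say so, and the Protocol's only schedule cannot meet its own definition.
- **That all PK parameters come from fast absorbers, or that the set is empty.** Step 5 shows otherwise for the main exposure measures, and the pre-4.0 set is not empty by construction.
- **That the 4-of-4 rule itself favours fast absorbers.** This would need unquantifiable values at 0.5 h, and no quantification limit or early concentration is given. A later peak does not imply it. Protocol 5.2.2.3 gives a mean steady-state AUC0-24 of 16,300 ng·hr/mL at 200 mg, an average of 16,300 / 24 ≈ 679 ng/mL, so carry-over makes it less likely at Week 4. It is possible, mainly on Day 1, but not shown.
- **That current-schedule subjects have no Week 4 trough.** Table 12 defines the trough as "Concentration at the end of the dosing interval". A steady-state pre-dose sample can be read as the end of the preceding interval.
- **That few higher-dose full profiles exist.** This is plausible: the higher dose opened on 12 March 2021 and version 4.0 is dated 8 April 2021. But no count is given, and under Protocol 15.1.1 sites adopt amendments only after approval.

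**Conclusion.** The point holds in two parts.

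The terminal-rate part follows from the sampling times alone: lambda_z, half-life, AUCinf, CL/F and Vz/F can be reported only for pre-4.0 profiles with Cmax at 0.5 h. That this subset is atypical, and possibly empty, rests on the food effect carrying over to this study. The food effect was seen with capsules in healthy volunteers; here subjects take tablets, and taking them without food is not a protocol deviation.

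The evaluable-set part is zero tolerance for a lost sample. Its size cannot be determined from the documents. At an assumed loss of 2% to 20% per sample, independent across samples, 92% to 41% of profiles remain. Whether the loss is related to absorption speed is open.

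This is a reporting defect in a secondary, descriptive analysis, and worth correcting before the PK tables are produced.

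**What to change.** 1. Remove lambda_z, half-life, AUCinf, CL/F and Vz/F from the noncompartmental summary tables and take them from the population PK analysis already planned in SAP 13.5.9. At minimum, report the number of profiles behind each and state that they are limited to profiles peaking at the first sample.
2. Redefine the PK Evaluable Set in SAP 11.3 by profile (Day 1 or Week 4), for the pre-4.0 schedule only, as at least 3 measurable post-dose concentrations including the 24-hour sample. State that an early value below the limit of quantification does not disqualify a profile. Amend the matching sentence in SAP 13.5.9.2.
3. Align Protocol 13.2, so that it no longer sets a threshold its own schedule cannot reach.

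The cost is wording and fewer rows in one PK table, with no new data. Some AUC values would rest on one point fewer; flag those profiles in the listing.

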11.4 Intent-to-Treat Analysis Set

The intent-to-treat (ITT) analysis set will include all randomized subjects. The ITT set will be used as the primary analysis set to summarize efficacy, PD, and clinical outcome parameters. Subjects will be analyzed according to their randomized treatment assignment.

11.5 Modified Intent-to-Treat Analysis Set

The modified intent-to-treat (mITT) analysis set will include all randomized subjects who had at least 1 VOC in the 12 months prior to randomization and have received at least one dose of study drug. The mITT set will be used for sensitivity analyses of efficacy, PD, and clinical outcome parameters. Subjects will be analyzed according to their randomized treatment assignment.

11.6 Per Protocol Analysis Set

The per protocol (PP) analysis set will include all subjects in the safety analysis set who had at least 1 VOC in the 12 months prior to randomization, completed at least 1 valid clinical outcomes assessment without major protocol deviations or events that would be expected to affect the analysis and did not discontinue prior to Week 24 for reasons other than AEs. Subjects will be analyzed according to the actual treatment they received. The PP set will be used for sensitivity analyses of efficacy, PD, and clinical outcome parameters.

Major protocol deviations and subjects (or data) excluded from the PP Analysis Set will be defined by the Sponsor in a blinded manner prior to database lock.

12.0 Overview of Planned Analyses

This section summarizes the planned analyses for efficacy, PD, PK and safety for the interim analysis (IA) and final analysis (FA). The statistical analyses, which will be performed on locked and cleaned data extracts, will include all data through protocol-specified analysis time points. The data cut-off for the IA are specified below. The DMC may recommend the discontinuation of a dose arm, due to safety, which will inform the highest tolerated dose. Selected personnel involved in the analysis and review of unblinded data for the IA will abstain from attending study conduct and operational meetings after the data has been unblinded for any reason. Detailed statistical methods are defined in [Section 13.0](#).

An IA will be performed after all subjects have reached Week 24 or terminated early. The FA will be performed after all subjects have completed the study. The critical significance levels for the IA and FA to maintain an overall two-sided type I error rate of 5% will be based on an O'Brien-Fleming boundary, calculated from a Lan-DeMets alpha spending function, based on the number of highest tolerated dose and placebo subjects used in the primary efficacy analysis in the ITT analysis set.

A summary of planned analysis for IA/FA are summarized in [Table 4](#) below.

Table 4 Planned Analyses for IA and FA

| | IA | FA |
|--|--|--|
| Disposition, Baseline and Disease Characteristics | Yes | Yes |
| Exposure | Yes | Yes |
| Concomitant and Prior Medications | | Yes |
| Primary Efficacy: Annualized Rate of VOCs | Yes, with Alpha spending - fixed sequence design [a] | Yes, with propagated Alpha from IA [a] |
| Key Secondary Efficacy: Time to first VOC and HbF Responder rate at Week 24 | Yes [b] | Yes [b] |
| Other Secondary Efficacy: Biomarkers and Specialty Hematology parameters | | Yes |
| Other Secondary Efficacy (Annualized rate of VOC-related hospitalizations, etc.) | | Yes |
| Other Secondary Efficacy: PROs (ASCQ-Me, PROPr, SCSES) | | Yes |
| Exploratory Efficacy | | Yes |
| Subgroup Analysis | | Yes |
| Safety (AEs, Laboratory, Vital Signs, ECGs, etc.) | Yes, selected outputs only | Yes |
| PK | Yes, selected outputs for plasma concentration only | Yes |

[a] Two-sided alpha spending at IA for primary efficacy analysis is 0.002. Propagated Alpha of 0.0494 is to be spent at FA.

[b] Statistical testing for key secondary efficacy will proceed only after the efficacy of the primary efficacy endpoint is demonstrated.

12.1 Hypothesis Testing

For the primary comparisons, the null hypothesis for each pairwise comparison will be that the treatment effect of the highest tolerated dose of IMR-687 is equal to that of placebo; the alternative hypothesis is then that the treatment effect of the highest tolerated dose of IMR-687 and that of placebo are not equal. P-values will thus be reported as two-sided.

[figure not shown]
Key secondary and other secondary efficacy analyses will involve the above hypothesis applied to the secondary efficacy endpoints.

